The proposed pilot study is a 3 year prospective, randomized, controlled comparison of a single treatment with carbon dioxide laser resurfacing vs. carbon dioxide resurfacing plus autologous epidermal skin graft from a non sun exposed site vs. control. Thirty subjects will receive treatment with each of the modalities on randomly-assigned portions of the treatment area. The primary measures of efficacy are (a) count of the number of actinic keratosis and non melanoma skin cancers, (b) blinded evaluation of severity from standard digital photographs taken before and after the treatments, and (c) change in histology before and after treatment: seen by grading and change of p53 immunostaining. Other study endpoints include time point to the next skin cancer is found in the treatment area, overall clinical appearance, change in mutant P53 of skin samples, and telomere length variability.

Safety measures include (a) pain, (b) scarring, (c) wound healing, (d) and infection

Subjects will be recruited through advertisements posted within the hospital(s), outpatient dermatology clinics and partners electronic mail.

Inclusion criteria

1. Subjects with ages between 18 and 85 years, male or female.
2. Subjects with at least 4 clinically diagnosed AKs per treatment site (up to 200 sq cm), excluding the face.
3. Subjects with history of at least 1 skin cancer within the past year
4. Willingness to participate in the study
5. Informed consent agreement signed by the subject
6. Willingness to follow the treatment schedule and post treatment care requirements
7. Willingness to not use topical or systemic (oral) TREATMENT medications including imiquimod, 5 Fluorouracil, photodynamic therapy, during the treatment period.
8. Has not had treatment for AKs in the treatment area for 4 weeks prior to enrollment

Exclusion criteria

1. Subjects with active skin cancer in the treatment area. Once the non-melanoma skin cancer has been treated, the subject can be immediately enrolled.
2. Infection of the area to be treated
3. An open wound in the area to be treated
4. Presence of suntan in the area to be treated, or active tanning during the study
5. Subjects who have taken medication known to induce photosensitivity in the previous 3 months
6. The patient has any contraindication to use of the CO2 laser
7. Subject is unable to comply with treatment, home care or follow-up visits
8. Subject is pregnant or breast feeding

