- II) Exam of the treatment area: AK count, evaluate for clinically appearing NMSC present; evidence of scarring, evidence of infection; evidence of healing . Also will get history from patient: visits to dermatologist? and treatments rendered? Will also review medical records to confirm the history.
- III) 6 scouting epidermal biopsies, using shave biopsy technique (from the treatment area) for histology and immunostaining. Will also bank a portion for PCR at the end of the study.
- IV) Adverse event evaluation
- V) Investigator assessments: wound assessment, overall clinical appearance

Follow-up Visits(6 months, 1 year, 1.5 year, 2 year, 2.5 year) (lasting 30 minutes each)

- I) Photography
- II) Exam of the treatment area: AK count, evaluate for clinically appearing NMSC present; evidence of scarring, evidence of infection; evidence of healing . Also will get history from patient: visits to dermatologist? and treatments rendered? Will also review medical records to confirm the history.
- III) Adverse event evaluation
- IV) Investigator assessments: overall clinical appearance

End of Study visit (3 year) (lasting 1.5 hours)

Patients will exit the study after 3 years

- II) Photography
- III) Exam of the treatment area: AK count, evaluate for clinically appearing NMSC present; evidence of scarring, evidence of infection; evidence of healing . Also will get history from patient: visits to dermatologist? and treatments rendered? Will also review medical records to confirm the history

- IV) **6 scouting epidermal biopsies, using shave biopsy technique (from the treatment area) for histology and immunostaining. Will also bank a portion for PCR at the end of the study.
- V) Adverse event evaluation
- VI) Investigator assessments: overall clinical appearance

** During the course of the study, the subjects will have a total of 18 scouting epidermal biopsies using the shave biopsy technique

Evaluation of Safety and Efficacy

Assessed by investigators (non-blinded) and by blinded evaluators (clinical photographs), periodically for 3 years after a single treatment session.

Reported by the Patients

Specific form is attached.

I. Side effects reported by the patient:

To assess major and minor side-effects, patients will be asked for each treatment site to fill in the following sentence for each test site: **“The side effects I experienced after the treatment were:”** E.G.

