Describe the plan for monitoring the data to ensure the safety of subjects. The plan should include a brief description of (1) the safety and/or efficacy data that will be reviewed; (2) the planned frequency of review; and (3) who will be responsible for this review and for determining whether the research should be altered or stopped. Include a brief description of any stopping rules for the study, when appropriate. Depending upon the risk, size and complexity of the study, the investigator, an expert group, an independent Data and Safety Monitoring Board (DSMB) or others might be assigned primary responsibility for this monitoring activity.

NOTE: Regardless of data and safety monitoring plans by the sponsor or others, the principal investigator is ultimately responsible for protecting the rights, safety, and welfare of subjects under his/her care.

The principal investigator and sub investigator will be responsible for the safety monitoring. Safety data will be collected at each visit of the study: adverse events, serious adverse events, side effects from treatment. The safety data will be reviewed every 3 months. SAE's will be dealt with immediately. It will be up to the investigator to develop the SAE to take immediate action. Efficacy data will be collected at each study visit. Blinded investigators will perform

overall efficacy assessments of this study. The Principal Investigator will be reviewing data on an ongoing and consistent basis throughout the duration of the study. The Principal Investigator is responsible for protecting the rights, safety, and welfare of subjects under his/her care. Principal investigator will be responsible for this review and for determining whether the research should be altered or stopped. If any severe adverse effect or death directly related to the treatment proposed occurs, Principal Investigator will report to the IRB and an expert group or an independent Data and Safety Monitoring Board (DSMB) or others might be assigned primary responsibility for this monitoring activity.

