Describe the plan to be followed by the Principal Investigator/study staff for review of adverse events experienced by subjects under his/her care, and when applicable, for review of sponsor safety reports and DSMB reports. Describe the plan for reporting adverse events to the sponsor and the Partners' IRB and, when applicable, for submitting sponsor safety reports and DSMB reports to the Partners' IRBs. When the investigator is also the sponsor of the IND/IDE, include the plan for reporting of adverse events to the FDA and, when applicable, to investigators at other sites.

NOTE: In addition to the adverse event reporting requirements of the sponsor, the principal investigator must follow the Partners Human Research Committee guidelines for Adverse Event Reporting

Any adverse events will be reviewed and analyzed by the Principal Investigator as soon as the event occurs and will be documented on Redcap. Any unanticipated problems involving risks to subjects or others including adverse events will be reported to the PHRC in accordance with PHRC unanticipated problems including adverse event reporting guidelines.

Patients will receive only one study treatment (visit 0). After that, no test site will receive study treatment (follow-ups). The patients will continue to have routine dermatologic care. If a pre-skin cancer, skin cancer, or other dermatologic disease develops within the treatment area or the control it will be treated with the standard of care by either the patient's dermatologist or the investigators of this study. Our study documents will note all treatments that are needed in the treatment area and the control. We expect that the control sites will not improve as much as treated sites, and they will serve also as a comparative endpoint.

MONITORING AND QUALITY ASSURANCE

Describe the plan to be followed by the principal investigator/study staff to monitor and assure the validity and integrity of the data and adherence to the IRB-approved protocol. Specify who will be responsible for monitoring, and the planned frequency of monitoring. For example, specify who will review the accuracy and completeness of case report form entries, source documents, and informed consent.

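### Primary measure (a), the AK/NMSC count, appears to fall to non-blinded investigators, and the protocol provides no blinded version of it

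*Protocol*

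**What the plan says.** Research Design and Methods in the protocol lists three primary measures. The first two are "count of the number of actinic keratosis and non melanoma skin cancers, (b) blinded evaluation of severity from standard digital photographs"; the third is "change in histology before and after treatment: seen by grading and change of p53 immunostaining". Blinding is attached to (b) and not to (a).

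The visit lists place the count in the live examination. From Week 4 to Year 3 the item reads "Exam of the treatment area: AK count, evaluate for clinically appearing NMSC present". From Month 3 the same item adds a check of the patient's treatment history against medical records.

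Evaluation of Safety and Efficacy divides the assessors: "Assessed by investigators (non-blinded) and by blinded evaluators (clinical photographs), periodically for 3 years after a single treatment session". The one form marked for a blinded physician is the Overall Appearance Scale, completed from photographs. Its columns are headed with the names of the three site conditions. The visit lists also give overall clinical appearance as an investigator assessment.

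Data and Safety Monitoring says "Blinded investigators will perform" the overall efficacy assessments of the study, a term it does not define. Later, under adverse event review, it says "We expect that the control sites will not improve as much as treated sites".

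**The concern.** An AK is called by eye and hand, and borderline lesions are a matter of judgement. In this design the three conditions lie on portions of one subject's skin. An unblinded examiner therefore knows what each portion received and sees the comparators at the same visit. A small, consistent difference in how doubtful lesions are called would appear as a treatment difference. Randomising the portions does not protect against this, because the error enters at assessment.

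The count carries Aim 1 (tumour burden) and Aim 3 (number of AKs). It also bears on Aim 2, the comparison of CO2 laser, CO2 laser plus graft, and control. The other two primary measures are useful, but neither counts lesions.

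**Working it through.** **Who makes the count**

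1. The count is an in-person examination item (visit lists, Week 4 to Year 3).
2. Blinded evaluators are tied to clinical photographs, and investigators are called non-blinded (Evaluation of Safety and Efficacy).
3. The only form assigned to a blinded rater is the Overall Appearance Scale, which corresponds to measure (b).
4. Nothing provides for a blinded examiner or for a count from photographs.
5. So the count falls to the non-blinded investigators. This is an inference from items 1 to 4, since no sentence names the counter.

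**Does Data and Safety Monitoring change this?** There are two readings. If its overall efficacy assessments include the count, it conflicts with item 2. If they mean only the photograph rating, it agrees with item 2 and measure (a) has no blinding. The text does not settle which is meant.

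**Could a blinded count use existing material?** The visit schedule marks both a photograph and an AK/NMSC count at baseline, Week 4, Months 3 and 6, and Years 1, 1.5, 2, 2.5 and 3. That is 9 occasions, 8 of them after treatment. The appearance form has a control column filled in from photographs, so control photographs are implied.

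**How much could differential counting matter?** The protocol gives 30 subjects but no alpha, effect size or standard deviation, so there is no figure to reproduce. The following is an illustration on assumed values:

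- a two-sided 5% paired comparison of two sites, with no true effect;
- Poisson counts with mean μ per site, where 4 is the entry minimum used as a mean and 8 is an arbitrary higher value;
- the treated site under-counted by a fraction b.

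Formulas: difference d = μb; SE = √[(μ + μ(1 − b))/30]; z = d/SE; rejection rate = 1 − Φ(1.96 − z) + Φ(−1.96 − z).

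Example with μ = 4 and b = 0.2: d = 0.8; SE = √(7.2/30) = 0.490; z = 1.633; rate = 37.2%.

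| Mean AKs per site | b = 0 | b = 10% | b = 20% | b = 30% |
|---|---|---|---|---|
| 4, formula | 5.0% | 12.5% | 37.2% | 71.2% |
| 4, simulation | 5.0% | 11.1% | 33.7% | 66.3% |
| 8, formula | 5.0% | 20.3% | 63.7% | 94.6% |
| 8, simulation | 4.9% | 18.4% | 58.5% | 91.7% |

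The simulation used 20,000 runs of a paired t-test, with a gamma subject effect shared by the two sites. It agrees closely enough for this purpose.

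**The case against.** The best defence is that this is a pilot with three primary measures, one of them expressly blinded and one histological. Laser effects may be visible, so full masking against control may be unattainable, live or in photographs. The stated expectation about control sites is the study hypothesis and is not evidence of biased counting. All of this is fair. It limits the point to measure (a) and limits what blinding can achieve, but it does not supply a blinded count.

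Several stronger readings are tempting, and the protocol does not support them:

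- **A flat contradiction on blinding.** A reader might take Data and Safety Monitoring to say that the counts are blinded. It speaks only of overall efficacy assessments, which may mean the photograph rating. It is an ambiguity to resolve.
- **NMSCs counted on appearance alone.** The visit check is of clinically apparent lesions. However, history is taken, records are reviewed from Month 3, and treatments in both the treatment area and the control are noted. The protocol is silent on pathological confirmation; it does not rule it out.
- **The whole efficacy result at risk.** Measures (b) and (c) do not rest on this count.
- **One lesion as 75% of a portion's count.** That figure spreads the minimum of 4 AKs over three portions (4/3 = 1.33; 1/1.33 = 75%). The appearance form uses treatment site for each lasered area separately. On that reading the minimum applies to each such area and the figure is 1/4 = 25%. Either way it describes one subject at the entry minimum and does not estimate bias across 30 subjects.

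**Conclusion.** The point holds for measure (a). On the protocol's own description it is a subjective, within-subject count made by non-blinded investigators, with no blinded counterpart. That they are the counters is a strong inference and not a stated fact.

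The size and direction of any bias are unknown. The rates of about 12% to 37% at mean 4, and 20% to 64% at mean 8, assume under-counting of 10% to 20%. They show only that modest differential counting would matter with 30 subjects. They do not predict what will happen in this trial. This is a worthwhile, inexpensive improvement and does not invalidate the design.

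**What to change.** 1. **Blinded count.** Have the existing blinded photograph evaluators also count AKs per portion on the photographs taken at baseline and at each counting visit from Week 4 to Year 3. Replace the treatment-named columns on their form with coded portion labels. Report the result as a blinded version of measure (a) beside the live count.
2. **Live count.** State who makes it. Where existing staffing allows, have it made before the interval treatment history is taken and by someone who did not treat that subject.
3. **NMSCs.** Report those confirmed by standard-care pathology, found through the planned record review, separately from those only suspected clinically. Keep the latter in the report. A confirmed-only rule would lose NMSCs managed without biopsy, and the decision to biopsy would remain unmasked in any case.
4. **Wording.** Reconcile Evaluation of Safety and Efficacy, the Overall Appearance Scale and Data and Safety Monitoring. Define the overall efficacy assessments, and say whether the appearance rating belongs to the investigator, the blinded physician or both.

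**Cost.** Wording changes, one extra line on the photograph form and some reading time: at most 30 subjects × 9 occasions × 3 portions = 810 portion counts. No visit or procedure is added. Photographs may miss lesions found by touch, and visible laser effects limit masking against control. The gain is therefore greatest for CO2 versus CO2 plus graft, where both portions were lasered.

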**PARTNERS HUMAN RESEARCH COMMITTEE
PROTOCOL SUMMARY**

Answer all questions accurately and completely in order to provide the PHRC with the relevant information to assess the risk-benefit ratio for the study. Do not leave sections blank.

PRINCIPAL/OVERALL INVESTIGATOR

[name]

PROTOCOL TITLE

Treatment of Field Cancerization for Reduction in Tumor Burden – A Prospective Study

NCT NUMBER

NCT02150863

FUNDING

Wellman Center for Photomedicine

VERSION DATE

December 28, 2016

SPECIFIC AIMS

Concisely state the objectives of the study and the hypothesis being tested.

This project aims to treat field cancerization in a manner that will reduce the tumor burden in patients with significant photodamage

1. To demonstrate that we can reduce the non melanoma skin tumor burden over time by treating the entire field of actinic keratoses and atypical keratinocytes.
2. To compare the efficacy and side effects of ablative CO2 laser resurfacing vs. ablative CO2 laser resurfacing plus post treatment suction blister epidermal grafts vs. control (no intervention).
3. To demonstrate a reduction in the number of actinic keratoses over time
4. To demonstrate an improvement in clinical appearance of the treatment area
5. To demonstrate a reduction in the degree of P53 mutations seen with histopathology
6. To demonstrate that subjects tolerate the treatment with few side effects
7. To demonstrate increased telomere length in treated areas

BACKGROUND AND SIGNIFICANCE

Provide a brief paragraph summarizing prior experience important for understanding the proposed study and procedures.

Field cancerization is a risk for any individual with excessive and prolonged sun exposure, immunosuppression, or exposure to radiation or carcinogens. We are very good at treating the skin cancer but if we leave behind the atypical field of keratinocytes it is only a matter of time

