until the next skin cancer needs to be excised. The current treatment regimens for treating AKs and SCCs involve frequent office visits with extensive cryotherapy, numerous biopsies and excisions. We often use topical medications to treat field cancerization, such as 5-fluorouracil or imiquimod. These treatments are often ineffective and need to be repeated frequently. The need for multiple treatments may be related to compliance. Often people cannot tolerate these treatment regimens. Thus there is the need for an optimized treatment regimen to improve clearing the field of atypia and precancerous lesions. This would cut down on cost, risks of surgical procedures, and patient discomfort.

We want to evaluate of effectiveness of ablative carbon dioxide (CO2) laser used to precisely remove the epidermis of an entire field, thus removing all the typical keratinocytes and basal stem cells that have been mutated. After the CO2 treatment a portion of the area treated would then be covered with autologous epidermal skin grafts from a non-exposed area (buttocks or thigh). We hypothesize that the epidermal skin grafts would not only improve/hasten the wound healing process after CO2 but it would also provide the field with stem cells that have yet to receive damaging radiation.

Ablative CO2 laser was first used by surgeons to cut and vaporize tissue. It then became a popular device with both surgeons and dermatologists for treatment of deep facial rhytides. More recently these lasers have been used to treat significantly photodamaged skin and actinic keratoses. The studies showing varying rates of reduced AK counts over short periods of time. The longest follow up being 2 years.

Suction blister autologous epidermal grafting is a simple procedure being used most commonly for vitiligo, but also wound healing and scarring. There are several IRB approved protocols at MGH already using this technique (PI: [name], MPH).

RESEARCH DESIGN AND METHODS

Briefly describe study design and anticipated enrollment, i.e., number of subjects to be enrolled by researchers study-wide and by Partners researchers. Provide a brief summary of the eligibility criteria (for example, age range, gender, medical condition). Include any local site restrictions, for example, "Enrollment at Partners will be limited to adults although the sponsor's protocol is open to both children and adults."

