The laser used is the Ultrapulse CO2 Laser (Lumenis). Patients will be treated according to the standard of care. The settings used for the CO2 laser will be commonly used settings that will ablate down to the bottom layer of the epidermis (8 – 20 J/cm²). Any remaining epidermis will be removed with saline soaked gauze. The papillary dermis has a characteristic glistening appearance and this will also be used as a treatment endpoint. If the papillary dermis is seen, the treatment in that area will be considered completed.

Participants or caregivers will be instructed to do saline soaked gauze soaks three times daily and apply Vaseline™ or Aquaphor™ onto the treated areas for up to 7 days post op as needed. Wound care instructions will be given to the patient, and a Day 3 follow-up visit will be scheduled.

Epidermal Blistering and Micrograft Preparation

A suction device will be applied to area of skin approximately 5.0 cm in diameter. This will be left in place approximately 30-40 minutes and may cause mild discomfort because of the suction. After the microblisters have been raised, the blister roofs (a superficial epidermal sample) with an average thickness of 200 microns and size of 1.75 mm in diameter will be removed and transferred to a sterile Tegaderm wound dressing that will be applied to the recipient site. The superficial donor wound will then covered with sterile Tegaderm or Duoderm.

Post- Procedure follow up Visits (Day 3, Day 7) (lasting 30 minutes)

- I) Photography

- II) Exam of the treatment area: wound check; evidence of scarring, evidence of infection; evidence of healing
- III) Adverse event evaluation
- IV) Investigator assessments: wound assessment, overall clinical appearance
- V) Patient assessments: pain scale and side effects

Follow-up Visits(Week 4) (lasting 30 minutes)

- I) Photography
- II) Exam of the treatment area: AK count, evaluate for clinically appearing NMSC present; evidence of scarring, evidence of infection; evidence of healing. Also will get history from patient: visits to dermatologist? and treatments rendered?.
- III) Adverse event evaluation
- IV) Investigator assessments: wound assessment, overall clinical appearance
- V) Patient assessments: Pain scale and side effects

Follow-up Visits

(Month 3) (lasting 1.5 hours)

- I) Photography

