Table I. **N/A:** Did not have this side effect / **1:** Mild / **2:** Moderate / **3:** Severe

A. Blistering	N/A	1	2	3
B. Scarring	N/A	1	2	3
1. Swelling	N/A	1	2	3
2. Redness	N/A	1	2	3
3. Scabs (crusting)	N/A	1	2	3
4. Weeping skin (pustulation)	N/A	1	2	3
5. Scaling or flaking skin (exfoliation)	N/A	1	2	3
6. Itchy skin	N/A	1	2	3
7. Erosion (ulceration)	N/A	1	2	3
8. Tanning	N/A	1	2	3
9. Lightening of the skin	N/A	1	2	3
11. Wheals	N/A	1	2	3
12. Bleeding	N/A	1	2	3
13. Folliculitis/ Acne	N/A	1	2	3
14. Oozing	N/A	1	2	3
15. Change in sensitivity/numbness	N/A	1	2	3

[figure not shown]
I. Pain assessment - Visual Analog Scale (VAS).

The VAS will be completed by study subject immediately after the treatment, and at each procedure follow up visit (Day 3, Day 7, week 4)

Pain is any of the following: sensation of tingling, stinging, prickling, or burning feeling, heat under the skin, tenderness, mild, moderate or severe pain).

Specific VAS form is attached

Patients will be asked to circle the number below that most closely corresponds to pain associated with their DISEASE.

Reported by the Investigators and Blinded-evaluators

Reported by the Investigator

Specific form is attached.

Investigator's Wound Assessment

Table 2. N/A: Did not have this side effect / 1: Mild / 2: Moderate / 3: Severe

A. Blistering	N/A	1	2	3
B. Scarring	N/A	1	2	3
1. Swelling	N/A	1	2	3
2. Redness	N/A	1	2	3
3. Crusting	N/A	1	2	3
4. Pustulation	N/A	1	2	3
5. Scaling or flaking skin (exfoliation)	N/A	1	2	3
6. Erosion (ulceration)	N/A	1	2	3
7. Hyperpigmentation	N/A	1	2	3
9. Hypopigmentation	N/A	1	2	3
10. Urticaria	N/A	1	2	3
11. Infection	N/A	1	2	3
12. Folliculitis/ Acne	N/A	1	2	3
14. Oozing	N/A	1	2	3

--	--

Overall Appearance Scale (blinded MD to complete with photos)

- Physicians will consider both cosmetic appearance but also the degree of photodamage and clinical atypia.

	Co2 treatment site	Co2 + epidermal graft Treatment site	Control site
Excellent	 5	 5	
Good	 4	 4	
Satisfactory	 3	 3	
Poor	 2	 2	
Unacceptable	 1	 1	

End points:

- AK count
- NMSC count
- change in overall clinical appearance
- time to healing

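### The patient side-effect item covers everything since treatment but is repeated at Day 3, Day 7 and Week 4, so on that form a resolved effect looks the same as a persisting one

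*Protocol*

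**What the plan says.** Under Evaluation of Safety and Efficacy, Reported by the Patients, the protocol states that "patients will be asked for each treatment site to fill in the following sentence for each test site". The wording that they are given to complete is "The side effects I experienced after the treatment were". Table I offers four answers per effect: N/A, defined as "Did not have this side effect", and grades 1 to 3 for mild, moderate and severe. The text gives no recall window, no category for an effect that has resolved, and no stop date. It adds "Specific form is attached", and that form is not part of the document at hand.

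The item is used three times. The Day 3 and Day 7 visits list "Patient assessments: pain scale and side effects", the Week 4 visit repeats this, and the schedule table agrees. Only one study treatment is given, on Day 0 (Data and Safety Monitoring).

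Two statements bear on how the answers will be used. Specific Aims, item 2, is "To compare the efficacy and side effects of ablative CO2 laser resurfacing vs. ablative CO2 laser resurfacing plus post treatment suction blister epidermal grafts", against an untreated control; item 6 is to show that side effects are few. Background and Significance hypothesises that the grafts "would not only improve/hasten the wound healing process after CO2".

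**The concern.** The stem is in the past tense and its window opens at the single treatment. The answer for no event says that the effect never happened. Once an effect has occurred, N/A is therefore untrue at every later visit, and the truthful answer at Week 4 includes effects that ended weeks before.

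A form given at three visits invites reading by visit. Under the literal wording, the share of sites with an effect can only stay level or rise from Day 3 to Week 4. Two sites that differ only in how long an effect lasted score the same. Shorter duration is one advantage to be expected of the graft if it speeds healing. Duration also matters in the protocol's own risk section, which treats redness or swelling beyond 3 days as a sign of infection.

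If some patients answer literally and others report how the site is today, the by-visit rates combine two quantities in unknown proportion.

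**Working it through.** **Step 1: what the wording implies.** Take two sites with an effect of the same worst grade, starting on Day 0. On site A it ends before Day 3; on site B it is still there at Week 4. The truthful records are:

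| | Day 3 | Day 7 | Week 4 |
|---|---|---|---|
| Site A, present at visit | no | no | no |
| Site B, present at visit | yes | yes | yes |
| Site A, item as worded | grade | grade | grade |
| Site B, item as worded | grade | grade | grade |

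The last two rows are identical. Whether the effect ever occurred, and its worst grade, are preserved; how long it lasted is not.

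**Step 2: which effects have another graded source.** Table I (patient) has 16 items. Table 2 (Investigator's Wound Assessment) has 14, is completed at an examination at Day 3, Day 7, Week 4 and Month 3, and does not carry the patient stem. Thirteen patient items have a counterpart there, counting scabs as crusting, tanning as hyperpigmentation, lightening as hypopigmentation and wheals as urticaria. Oozing is among them. That leaves 16 − 13 = 3 items that only the patient table grades: itchy skin, bleeding, and change in sensitivity/numbness. The protocol lists itching and bleeding as common after CO2 laser.

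**Step 3: illustration of size.** The protocol states no rate or duration, so there is no figure to reproduce. Assume that 80% of sites are affected from Day 0, that durations are exponential with mean m days, and that every patient answers literally.

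Present at visit day t: 0.8 × exp(−t/m). Item as worded: 0.8 at every visit, for any m.

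| m (days) | Day 3 | Day 7 | Week 4 (day 28) |
|---|---|---|---|
| 3 | 0.294 | 0.078 | 0.000 |
| 5 | 0.439 | 0.197 | 0.003 |
| 10 | 0.593 | 0.397 | 0.049 |
| 14 | 0.646 | 0.485 | 0.108 |
| as worded | 0.800 | 0.800 | 0.800 |

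If grafting halved the mean duration from 10 to 5 days, the differences in presence would be 0.593 − 0.439 = 0.154 at Day 3, 0.397 − 0.197 = 0.200 at Day 7 and 0.049 − 0.003 = 0.046 at Week 4. The item as worded records 0 at each. Read as current presence, it overstates Week 4 by 0.800 − 0.108 = 0.69 (m = 14) to 0.800 − 0.000 = 0.80 (m = 3).

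A second set of assumptions gives the same picture. With every site affected and median durations of 5 days (graft) and 8 days (CO2 alone), presence at Day 7 is 2^(−7/5) = 38% against 2^(−7/8) = 55%; the item as worded gives 100% against 100%.

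**The case against.** The strongest reply is that the trial does not depend on this form to see healing. It has the investigator's wound assessment, an exam for healing at follow-up visits, photographs, adverse event evaluation, and time to healing as a listed endpoint that nothing ties to the patient form. This stands. A reader might infer that faster resolution on the grafted site cannot show anywhere in the trial, and the documents do not support that. The reply is weaker for the three patient-only items: photographs and a wound exam do not show itching or numbness, and the pain scale has no row for them. Adverse event records might date some of these effects, but the protocol does not say what they contain.

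Second, the full form is attached and not shown. One might infer that it has no date or present-today field; that cannot be checked. What can be said is that the protocol text sets none.

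Third, a cumulative report with a grade serves Aims 2 and 6 through incidence and severity, and repeating it catches late effects. This stands for incidence and worst grade, provided all patients read the stem alike. Repetition then adds time of onset and fresher recall, but not resolution.

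Fourth, a reader might infer that one event will be counted up to three times. The protocol describes no such tabulation, and how the form is analysed may properly sit in an analysis plan. The point concerns what the item captures; resolution that was never recorded cannot be recovered by any analysis of this item.

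**Conclusion.** The point holds for the patient form as the protocol words it. The recall period runs from Day 0 at all three visits, so persistence and resolution cannot be told apart on that form, and mixed readings by patients would blur the by-visit rates. Incidence and worst grade per site remain comparable under a consistent cumulative reading.

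The loss is minor to moderate. It concerns a safety measure and falls mainly on itching, bleeding and change in sensitivity or numbness. The prevalence figures are illustrations: the 80% rate, the exponential durations and the halving by graft are all assumed, and the recorded difference of zero needs every patient to answer literally. They show the direction and possible scale of the masking and do not predict the trial's results. The conclusion would lapse if the attached form already sets a recall period; only the protocol wording would then need correcting.

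**What to change.** Reword the stem so that each form covers its own interval, for example: *At this site, since my last study visit (at Day 3: since the treatment), I had:* with the worst grade in that interval. Add one column: *still present today: yes/no*. Both parts are needed, because at Day 3 the new interval is the same as the old one and only the added column separates resolved from persisting effects.

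Report current prevalence by visit from the new column, and count each effect once per site for incidence. If the attached form already defines the recall period, align the protocol text with it instead.

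The cost is an edit to an existing REDCap form, a slightly longer form for patients and a minor IRB amendment. Forms already completed under the present stem must be analysed as cumulative. No visits, staff or procedures are added.
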